5.3 Method for Assigning Subjects to Treatment Groups

All subjects will receive the same drug protocol in a double-blind, cross over fashion. The study biostatistician will create a randomization table. Subjects will be randomized into two arms by permuted block of small size 2 with 1:1 ratio and maximum imbalance of 1. We will also restrict E2-P4 group to have the n = 8 and P4-E2 to have n=7 because the response from E2-P4 group is the primary phase of interest. The pre-generated randomization sequence will be uploaded to REDCap, with assignment group information coded. REDCap will randomly assign a possible number from table when a subject is entered. Study personnel will only receive that randomization number and will not receive information on the coded assignment group, so not only will they not know what group a subject is in, but they won't know which subjects have been similarly assigned. We will

not store any information on what assignment groups codes actually correspond to in REDCap, further ensuring that randomization remains concealed.

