7.1 Sample Size Determination

This is a pilot study to obtain pilot data for larger studies. Previous observational studies in humans suggest at least a moderate effect of ovarian hormones on binge eating with an effect size approximating $d = 1.5$,^{5, 196, 197} including [name] pilot work described above. Additionally, [name] pilot work of E2 treatment in midlife women indicates $d = 2.3$ for the effect of E2 replacement decreasing appetite in women with and without major depression whereas other published work showed $d = 1.51$ for the effect of Lupron on decreasing food cravings in women with PMS.⁸⁷ Because we are directly manipulating ovarian hormones with an experimental design, which removes other potential confounds found in observational studies, we expect that the effect sizes from observational studies are an underestimate.

According to a power estimation for Aims 1 and 2, with a projected sample of $n = 15$, an effect size of .77 is required to detect a treatment difference at a two-sided .05 significance level at 80% power (calculated based off of projected sample size and desired power). Additionally, based on $n = 15$ and estimated effect size of 1.5 for E2 on binge eating (the average effect size observed in previous studies),^{5, 196, 197} a power estimation for Aim 1 (our primary aim) estimates our power at significance of .05 is $> 90\%$. Thus, despite the smaller sample size of this pilot study, power analyses indicate we should have sufficient power based on hypothesized effect sizes (which are empirically based) for E2 on binge eating.

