The BIS/BAS and SPSRQ will be included as a self-report measures of reward response. Specifically, we will include the reward responsiveness, behavioral inhibition, and fun seeking subscales of the BIS/BAS as self-report correlates of the reward response. The SPSRQ will be used to assess sensitivity to reward.

Hypothesis. Our overarching hypothesis for the following aims is that BN represents a hormone sensitive phenotype and this sensitivity is displayed as an impaired reward response within the context of low E2 such that E2 addback will be beneficial for all outcomes of interest (i.e., binge eating, aspects of the reward response). As such, our null hypothesis is that there is no effect of E2 on binge eating or the reward response. For all hypothesis tests, we will use the Benjamini-Hochberg Procedure to correct for multiple comparisons.

Aim 1: Quantify the direct effect of E2 and P4 on binge eating in women with BN.

Dependent variables: EPSI binge eating subscale score; DSRP binge eating weekly average.

Independent variables: Treatment sequence, treatment condition, and selected covariates

The two longitudinal measures of binge eating (i.e., EPSI subscale score and DSRP weekly average) will be fit to linear mixed effect models with subject-specific random intercept assuming an unstructured covariance among different time points. Such a covariance allows different variance and covariance parameters to be estimated for each time point allowing for potential increasing or decreasing variability in outcomes during each of the follow-up time points for each outcome and will include fixed effect predictors such as binary treatment sequence (E2-P4 or P4-E2) and treatment condition of categorical variable with three levels: Lupron-alone, E2, or P4, where effect size and standard error of fixed effect parameters will be estimated in the described model followed by t -test. Study hypotheses comparing outcomes between group outcomes of E2 vs. Lupron-alone, E2 vs. P4, and P4 vs. Lupron-alone, will be tested using contrasts test through t -test of least squares means estimate in the context of the main effects model.

Along with the primary contrasts of interest described above, additional contrasts between each end point of treatment condition (Lupron-alone, E2, or P2) and baseline (T1), which occurs prior to medication administration, will be tested using the statistical model just described above.

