If Aims 1 and 2 alternative hypotheses are supported, we will conduct a tertiary exploration to address whether changes in reward behavior mediate the link between E2 addback and changes of binge eating. A four-step mediation analysis (Baron & Kenny 1986) will be applied to preliminarily investigate the mediation effect of reward-motivated behavior on changes of binge eating. An approximated t-test will be used to test the significance of the mediation effect.

Missingness. We will use multiple imputation to correct for data determined to be missing at random. Data for any dropouts will be compared with data for those who complete the study to determine the extent to which excluding their data will introduce selection bias, and selection bias will be identified as a weakness in any resulting publications or presentations.

Sensitivity Analysis. In addition to the statistical tests described above, we will use sensitivity analyses to evaluate the robustness of the main results of the study to reasonable perturbations of the statistical methods and assumptions used and to help ensure reproducibility of the main results. Sensitivity analysis will address the inclusion/exclusion of questionable data values (i.e., outliers), the use of alternative methods of coping with missing values and dropouts, and modeling assumptions. We will additionally examine whether associations differ based on the severity (e.g., DSM-5 mild, moderate, severe, extreme) of baseline binge eating and purging frequency.

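### If the approximate t-test for mediation is a Sobel-type test, it is much too conservative at n = 15; joint significance with a Monte Carlo interval, reported unconditionally, would serve better

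*Combined protocol and SAP*

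**What the plan says.** The mediation analysis comes at the end of Aim 3 in section 7.2 and is conditional: "If Aims 1 and 2 alternative hypotheses are supported, we will conduct a tertiary exploration". The method is named: "A four-step mediation analysis (Baron & Kenny 1986) will be applied to preliminarily investigate the mediation effect". The decision rule is one sentence: "An approximated t-test will be used to test the significance of the mediation effect". The plan gives no standard error formula, degrees of freedom or interval for the indirect effect. It plans no estimate for the case where Aim 1 or Aim 2 fails.

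The plan does not define when an aim counts as supported. Aim 1 has two outcomes and several contrasts, and Aim 2 has several measures. Section 7.2 adds: "For all hypothesis tests, we will use the Benjamini-Hochberg Procedure to correct for multiple comparisons".

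The change-score correlation in Aim 3 does not depend on Aims 1 and 2. It bears only on the reward-to-binge path, uses self-report measures and takes baseline as comparator.

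On size, section 5.3 sets the groups: "We will also restrict E2-P4 group to have the n = 8 and P4-E2 to have n=7". Section 7.1 says that "an effect size of .77 is required to detect a treatment difference at a two-sided .05 significance level at 80% power" and cites an "estimated effect size of 1.5 for E2 on binge eating". No effect is given for the reward measures or for the link from reward to binge eating, and no power is stated for mediation.

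**The concern.** The indirect effect is a product of two estimates: E2 to reward (path a) and reward to binge eating (path b). In small samples the product divided by its first-order standard error does not follow a t distribution, and the usual critical value is too strict. Real mediation would then often be reported as not significant, with no interval to show how little the data could exclude.

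The precondition adds selection. An estimate that appears only after two significant results tends to be too large.

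Reward response is the proposed mechanism in this protocol, so a misleading negative would matter, even in an exploratory analysis.

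**Working it through.** **1. The plan's own figure.** Paired t-test, n = 15, 14 df, noncentrality d√15, two-sided .05.
- d = 0.77: noncentrality 2.98, power 79.2% (stated 80%). The effect giving exactly 80% is 0.778 (stated .77).
- d = 1.5: noncentrality 5.81, power 99.97% (stated above 90%).

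Both reproduce, so the stated effects are standardised within-woman differences. The paths below use the same scale.

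**2. Model (assumed).** For each woman take the E2-minus-comparator differences in mediator and outcome, each with SD 1:
- dM = a + error
- dY = c′ + b·dM + error, with total effect c′ + ab

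The range for a is 0.3 to 1.5, centred on the plan's 0.77; b is .3 to .7.

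**3. The tests.** Let z_a = â/se_a (14 df) and z_b = b̂/se_b (13 df).
- Sobel-type: T = âb̂ / √(b̂²se_a² + â²se_b²) = z_a·z_b / √(z_a² + z_b²), referred to t with 13 df (critical value 2.160).
- Joint significance: |z_a| > 2.145 and |z_b| > 2.160.

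|T| is always below the smaller of |z_a| and |z_b|. So whenever T rejects, joint significance rejects too, but not the reverse. If the two ratios are equal, each must reach 2.160 × √2 = 3.05 before T rejects.

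Example at a = 0.77, b = .5: z_a = 0.77 × √15 = 2.98. With se_b ≈ √(0.75/14) = 0.231, z_b = 2.16. Then T = (2.98 × 2.16)/√(8.88 + 4.67) = 6.44/3.68 = 1.75, well short of 2.160, although each path is at or past its own threshold.

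**4. Simulation.** 40,000 runs per scenario (fewer where intervals were computed), n = 15, unadjusted .05. The precondition is simulated as one significant paired t-test each for dM and dY. T and joint significance do not involve c′, so the total effect matters only for the precondition.

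| a | slope b | total effect | T alone | precondition and T | joint significance, no precondition |
|---|---|---|---|---|---|
| 0.5 | .5 | 0.77 | 7% | 6% | 20% |
| 0.77 | .5 | 0.77 | 18% | 16% | 38% |
| 0.77 | .5 | 1.5 | 18% | 18% | 38% |
| 0.77 | .5 | 0.385 (no direct effect) | 18% | 7% | 38% |
| 0.77 | .6 | 1.5 | 32% | 32% | 54% |
| 1.0 | .6 | 1.5 | 49% | 49% | 66% |
| 1.5 | .6 | 1.5 | 64% | 64% | 70% |
| 0.77 | 0 (no mediation) | 0.77 | 1.3% | 1.0% | 4% |

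**5. Splitting the loss** (a = 0.77, b = .5, total 0.77). Joint significance has 38%. Adding the precondition to it gives 32%; switching to T instead gives 18%; both together give 16%. The test does most of the damage. At a total effect of 1.5 the precondition costs nothing beyond the test of path a. It matters more when the total effect is small, as in the 0.385 row.

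**6. Inflation from the precondition alone** (mean estimate over true value, b = .5): 2.1 at a = 0.3, 1.4 at 0.5, 1.1 at 0.77, about 1.03 at 1.0, and 1.00 at 1.5.

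**7. Interval methods when b = 0 and a = 0.77** (nominal 5%): the percentile bootstrap rejects 7.5%. Monte Carlo with normal draws rejects about 5–6%, and with t-distributed draws about 3%. With t draws, power at a = 0.77, b = .6 is about 50%.

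**The case against.** The strongest reply is that this is a tertiary analysis, labelled preliminary, and that the plan never says which t-test it means. Asking for an overall effect and a mediator effect first belongs to the named four-step approach and is not an oversight. Joint significance itself needs a significant path a, so it keeps the mediator half of that condition. At the plan's expected 1.5 SD for binge eating, with a similar effect on reward, little is lost. And the change leaves mediation underpowered: 38% in the central case.

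Most of this stands, and it limits the point to a cheap improvement. It does not rescue the test. The 1.5 is for binge eating only; with reward at 0.77 SD the comparison is still 18–32% against 38–54%.

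Three stronger readings are tempting, and the documents do not support them.
- A reader might infer that the design halves mediation power as such. That depends on assumed paths, and the gap nearly closes at 1.5 SD on both effects.
- A reader might infer that an inflated estimate will be carried into the next trial. Section 7.1 says "This is a pilot study to obtain pilot data for larger studies", but nothing says that the mediation estimate is carried forward. The near-doubling of the estimate (1.85 in the central case) arises only if it is also selected on a significant t-test, which the plan does not state.
- A reader might infer that the result holds for any mediation model. Only within-woman differences were examined.

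**Conclusion.** The point holds as a minor one. If the unspecified test is the first-order product test, it is much too conservative at n = 15. Near the plan's own detectable effect it has about 18–32% power where joint significance has 38–54%. With a real path a and no path b it rejects about 1% of the time. The loss shrinks to 64% against 70% when both E2 effects are 1.5 SD and the slope is .6.

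The precondition is usually the lesser problem. It costs no extra power when the binge-eating effect is near 1.5. Its inflation of the estimate is about 10% at 0.77 SD, about 40% at 0.5 SD and negligible from 1.0 SD.

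These figures rest on assumed paths, on the Sobel-type reading with 13 df, and on one unadjusted test per aim for the precondition. Counting any measure as support would loosen that condition; requiring all measures, or applying Benjamini-Hochberg, would tighten it. No conclusion under Aims 1 or 2 is affected.

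**What to change.** In section 7.2, replace the approximate t-test with joint significance of the two paths. Add a Monte Carlo confidence interval for the indirect effect: draw each path as its estimate plus its standard error times a t variate on that path's residual degrees of freedom, and take percentiles of the product. Do not substitute a percentile bootstrap, which over-rejects at this sample size.

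Report the estimate and interval as exploratory whether or not Aims 1 and 2 are significant. Reporting would then no longer hang on the undefined meaning of support for those aims.

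The cost is two sentences, with no new data or participants. The downside is a wide exploratory interval in the report even when Aims 1 and 2 are null, and power for mediation that stays low.

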7.3 Subject Population(s) for Analysis

Most studies addressing the impact of ovarian hormones on binge eating have included heterogenous samples. While this increases generalizability, findings may be less robust or inconsistent because associations between variables of interest may differ by sub-groups within these populations. Specifically, we hypothesize these individuals would vary in their baseline dopamine activity which, in turn, would affect whether E2 has a beneficial or worsening effect on symptoms: the behavioral effect of E2 would not be consistent unless individual differences in dopamine are accounted for. This may account for why when samples are separated by high and low pathology (with higher pathology predicted to represent low dopamine), low E2 is consistently the catalyst for increased symptomatology.^{5, 12} Thus, the sample for this proof of concept study is focused on a clinical population of BN, a sub-group proxy for low baseline dopamine.

8 Ethical Considerations

This study is to be conducted according to US and international standards of Good Clinical Practice (FDA Title 21 part 312 and International Conference on Harmonization guidelines), applicable government regulations and Institutional research policies and procedures.

This protocol and any amendments will be submitted to a properly constituted independent Ethics Committee (EC) or Institutional Review Board (IRB), in agreement with local legal prescriptions, for formal approval of the study conduct. The decision of the EC/IRB concerning the conduct of the study will be made in writing to the investigator and a copy of this decision will be provided to the sponsor before commencement of this study. The investigator should provide a list of EC/IRB members and their affiliate to the sponsor.

All subjects for this study will be provided a consent form describing this study and providing sufficient information for subjects to make an informed decision about their participation in this study. See Attachment for a copy of the Subject Informed Consent Form. This consent form will be submitted with the protocol for review and approval by the EC/IRB for the study. The formal consent of a subject, using the EC/IRB- approved consent form, must be obtained before that subject undergoes any study procedure. The consent form must be signed by the subject or legally acceptable surrogate, and the investigator-designated research professional obtaining the consent.

9 Study Finances

9.1 Funding Source

This study is financed through a R21 grant from the National Institutes of Health.

9.2 Conflict of Interest

Any investigator who has a conflict of interest with this study (patent ownership, royalties, or financial gain greater than the minimum allowable by their institution, etc.) will have the conflict reviewed by a properly constituted Conflict of Interest Committee with a Committee-sanctioned conflict management plan that has been reviewed and approved by the study sponsor prior to participation in this study. All UNC investigators will follow the University conflict of interest policy.

9.3 Subject Stipends or Payments

Participants will be compensated \$900 upon completion of the study according to the schedule below. For study visits that occur at UNC, parking vouchers will be provided as well as mileage reimbursement for study. Payment is processed through the UNC Department of Psychiatry.

| Long Study Visits | |
|---|-------|
| Clinical Health Screening Visit | \$20 |
| Long Visit 1 (before medication administration) | \$50 |
| Long Visit 2 (during medication administration) | \$75 |
| Long Visit 3 (during medication administration) | \$75 |
| Long Visit 4 (during medication administration) | \$75 |
| Other Study Activities | |
| GYN exam | \$30 |
| Screening phase (1 menstrual cycle) | \$30 |
| Short Clinic Visits (3 visits, \$20/each) | \$60 |
| Lupron Injection (3 injections, \$5/each) | \$15 |
| Completion of daily survey and medication adherence during hormone challenge (\$5.00/day for 91 days) | \$455 |
| Follow-up Survey | \$15 |

10 References

1. American Psychiatric Association, *Diagnostic and Statistical Manual of Mental Disorders. Fifth Edition* 2013, Washington, DC: American Psychiatric Press.
4. [name], JH, Girdler, SS, and Bulik, CM. The role of reproductive hormones in the development and maintenance of eating disorders. *Expert Rev Obstet Gynecol*. 2012;7(6):573-583.
7. [name], JH and Runfola, CD. Eating disorders in midlife women: A perimenopausal eating disorder? *Maturitas*. 2016;85:112-116.
8. Asarian, L and Geary, N. Modulation of appetite by gonadal steroid hormones. *Philos Trans R Soc Lond B Biol Sci*. 2006;361(1471):1251-1263.
9. Eckel, LA. The ovarian hormone estradiol plays a crucial role in the control of food intake in females. *Physiol Behav*. 2011;104(4):517-524.

Appendix A. Flow Chart of Study Procedures

Appendix B. COVID Procedures

Appendix A. Study Procedures Flow Chart

Figure 5. Within-Subject Hormone Challenge (study visits occur every 2 weeks)

Appendix B. COVID Response

Due to the COVID-19 pandemic, this study will be modified as described below. These procedures are only in response to the COVID-19 pandemic. If we are able to begin recruitment, enrollment, and study visits ‘as usual,’ study procedures will resume as described in the original protocol.

All remote portions of study visits will be conducted via WebEx calls. All scheduled WebEx visits will be password protected and only those with the password can enter the call. WebEx has been approved by the UNC ITS as secure programs for PHI and sensitive information and the School of Medicine specifically recommends the use of WebEx for research study visits. WebEx is HIPPA complaint, ISO/IEC 27001:2013 certified, and approved for the transmission of PHI. Visits will be password protected and only those with the password can enter the study visit. Although Internet access is not a specific inclusion/exclusion criteria, because COVID19 requires converting many aspects of this study to virtual visits, we acknowledge participants will need to have access to the Internet.

Overview:

Recruitment will be conducted as described, we will make no changes to our recruitment procedures or methods. We previously created a modification for participants who appear eligible on a study screener to be added to a research study waiting list and will be re-contacted once the study is able to resume in-person visits. Once our revised study protocol is IRB approved, we will no longer create this waiting list and study enrollment will begin as described in this revised, COVID19 protocol addendum.

This current addendum includes our plans to begin enrolling participants and the updated measures to prevent against the spread of SARS-CoV-2. We have altered study activities to make many of them remote. When contact is essential for certain activities, we have included procedures to protect participants and our study team. We are limiting the number of study personnel that conduct in-person visits to two individuals—the Clinical Translational Research Center nurse and coordinator. Both will be dressed in personal protective equipment (PPE) and will follow procedures to prevent the opportunity of transmission.

PPE. During all interactions with participants, participants will be given a surgical mask and the study personnel will wear scrubs, gloves, and a surgical mask. Eye protection will be worn during Lupron injection and during blood draws. All items will be immediately removed as soon as possible after the study visit and washed or thrown away.

COVID screening. A COVID health check will be completed with all participants 24 hours prior to study visit. If this is not completed, the study visit will not occur. In addition, a departmental Qualtrics survey will be completed by research personnel prior to any study visits or interactions with human subjects, regardless of the location.

Preventive procedures. Study personnel, additionally, will follow preventive procedures. All equipment that will be shared between a participant and research staff (except paper) will be cleaned immediately prior to the study visit, immediately after use, and upon returning to CEED.

Social distancing. Distance will be maintained between people any time closer contact is not absolutely required (e.g., blood draws). As allowable, study visits will be scheduled as in-home. If a subject prefers to come to the hospital for a study visit, this request will be considered. As much of a study visit that can be completed without being in person will occur remotely in order to decrease interaction with subjects.

Study Activities

Recruitment & Eligibility

Distance. Due to the need to complete as many study visits offsite as possible, we have expanded our radius for in-home study visits to a radius of approximately 45 miles or 1-hour of UNC Hospitals (as described in the consent form). Although this change is in response to COVID19, for fairness, this will remain a permanent change to the study protocol.

Eligibility Screening: We will screen individuals remotely via Qualtrics and telephone as described in the original protocol. This includes screening individuals via phone or online Qualtrics screener. As previously approved, we were screening participants and adding them to a waitlist to be contacted once in-person visits resumed. Now that we are planning in-person visits, the individuals that were on the waitlist will be contacted to confirm study eligibility. A portion of the phone/clinic eligibility screener will be used to confirm eligibility. These participants will only be asked the menstrual cycle status and eating behaviors sections of the screener. In the event study activities need to be suspended again due to COVID19, we will resume use of the waitlist. This waitlist is a password-protected document that contains the potential subjects' name, temporary ID, and contact information.

Enrollment: If participants are deemed eligible based on their screening, we will follow-up with a remote Informed Consent (T0a) and a remote Clinical Health Screening and SCID Interview (T0b) visit. T0b will be scheduled after informed consent is obtained and the signed consent forms are received by study staff. No study procedures will be conducted until the signed consent forms are received by study staff. We also added 3 questions to the T0 questionnaires survey that assess the impacts of COVID-19 on eating behaviors.

Informed consent. The informed consent documents have been modified to reflect the changes to the study protocol outlined below. [name] or her trained study coordinator will obtain informed consent from those individuals who pass the initial screening and are interested in participating. Notably, the informed consent process during COVID (virtual/remote) will mirror the procedures for an in-person visit, the major difference being the visit will occur remotely via WebEx and the consent forms will be mailed, reviewed, signed, and mailed back. Participants will not review the consent documents on their own, but will be walked through the forms, verbatim, as would be completed during an in-person visit.

Two copies of the consent forms will be mailed to the person in unmarked envelopes. For any participant that does not receive this most recent consent form, they will be given the COVID-19 Consent Addendum. This document includes text from the updated study consent form that discusses COVID-19 exposure risks and the measures that may be taken to prevent exposure.

Consent forms will be reviewed remotely during WebEx (or telephone if necessary) and will be returned to study staff signed in a pre-paid envelope. The participant will be given multiple opportunities to ask questions. Prior to signing the consent form, participants will be asked the consent quiz to ensure understanding of the consent form. We will obtain contact information and social security number verbally from the participant after the consent process. Contact information and social security number are only required if the participant consents to participate in the study. Future studies consent will also only be obtained verbally.

Regarding WedEx, it is HIPPA complaint, ISO/IEC 27001:2013 certified, and approved for the transmission of PHI. Visits will be password protected and only those with the password can enter the study visit. UNC SOM specifically recommends the use of WebEx for virtual research study visits.

Study Procedures and COVID19 Study Visit Modifications:

Screening Period Prior to Medication Administration. Prior to medication administration, participants complete a screening period which examines their eating disorder symptoms daily, during 1 menstrual cycle. No changes have been made to this aspect of the protocol as the original protocol included completing this screening virtually/remotely through daily Qualtrics surveys.

Study Questionnaires. A majority of study questionnaires were already completed through Qualtrics so this is easily converted to remote completion. Two surveys, IDAS and EDE-Q, have moved from paper and pencil versions to Qualtrics during COVID-19. These are used to monitor safety throughout the duration of the study and will be scored automatically for study staff to review within the survey flow. When the study returns standard procedures, we will keep the option of completing these in Qualtrics or completing them in their paper/pencil versions. The Delay Discounting questionnaire has now been added to T1-T5 Qualtrics surveys. This would have previously been completed via a paper and pencil survey, but now will be completed electronically via Qualtrics. This will remain a permanent change. The COVID Stress Scale (CSS) has been added to the electronic questionnaires for each in person visit that includes in-person behavioral tasks (T1, T2, T3, T4) to assess distress in relation to COVID-19 during tasks.

Side Effect Checks and Interviews. The side effects and adherence interview will be conducted via interview through WebEx. Participants responses to the daily surveys will continue to be monitored daily and participants endorsing any concerning symptoms will be followed up with by the PI (as outlined in the original protocol).

Behavioral Tasks. Behavioral tasks must be completed in person due to the software used (i.e., E-prime). Although a remote option for E-prime is available, it is not ideal for tasks that are based on response time this could vastly differ across computers and operating systems. Using our computer standardizes this. The remote version also saves the data directly to the participants computer and requires it to be transferred to the study staff. This would also require participants have access to an appropriate computer.

Before using the study laptop, the research coordinator will thoroughly wipe down the entire laptop, especially the parts that are frequently touched. When setting up the tasks for the participant, the coordinator will wear gloves. Directions will be given to the participant at a distance, and the participant and coordinator will remain 6 feet apart whenever possible during this task. The Pre-Behavioral Task Food Intake Questionnaire will be completed with the participant by the study coordinator. In the event we must stop completing behavioral tasks in person, we will use the software application Millisecond as a back-up. Notably, our initial IRB approval proposed to use Millisecond; however, we converted to E-prime given we intend to include fMRI imaging in our future studies and UNC imaging center uses E-prime to run imaging tasks.

Millisecond allows for psychological tasks to be administered online, on any device able to download the application, and provides centralized and secure storage for data. Their servers are protected by high-end firewall systems, and scans are performed regularly to ensure that any vulnerabilities are quickly found and patched. All services have quick failover points and redundant hardware, with complete backups performed nightly. Data are stored redundantly across data centers for resiliency and availability during disasters. Millisecond provides each customer a unique username and strong

password that must be entered each time a customer logs on. The user remains authenticated only for the duration of the session and is automatically logged off after 30 minutes of inactivity. This system ensures that customer data can only be accessed by authenticated and authorized users. Customer data are processed and stored in world-class data center facilities in Oregon, USA. Data are not moved around to other locations. The data centers are housed in nondescript facilities. Physical access is strictly controlled both at the perimeter and at building ingress points by professional security staff utilizing video surveillance, intrusion detection systems, and other electronic means. Authorized staff must pass two-factor authentication a minimum of two times to access data center floors. All visitors and contractors are required to present identification and are signed in and continually escorted by authorized staff. The servers reside behind high-availability firewalls and are monitored using state of the art systems for detection and prevention of various threats including denial of service, man in the middle, IP spoofing, port scanning, and packet sniffing. Automated network security audits using the industry standard SSAE-16 method are conducted to the standards and requirements of the SANS/FBI security test, the U.S. Department of Homeland Security's published recommendations and the Payment Card Industry Data Security Standard. Millisecond encrypts all data in transit by enforcing Transport Layer Security (TLS) encryption (also known as HTTPS). Millisecond encrypts all data at rest using the industry standard AES-256 cypher. Millisecond deploys the general requirements set forth by many Federal Acts, including the FISMA Act of 2002. They meet or exceed the minimum requirements as outlined in FIPS Publication 200. HITECH (Health Information Technology for Economic and Clinical Health Act) updated HIPAA rules to ensure that data are properly protected and best security practices followed. Millisecond safeguards all customer data, and uses secure data centers to ensure the highest protection as per HITECH requirements.

Medication administration. Medication will be administered similar to our original protocol as in person contact is required (i.e., Lupron injection). However, for any study visits where giving the study participant their next set of oral medications is the *only in-person activity* needed, the study coordinator will pass off the pills directly to the participant during a drive by the participant's house. Alternatively, the participant can drive by the hospital and the research assistant will give them the pills when they pull up to the hospital. If the visit is already requiring in-person contact for another reason (i.e. Lupron injection or behavioral tasks), the personnel that is involved in the visit will give the participant the study pills.

Blood draws. Due to significant safety concerns regarding in-person contact and biological specimen processing and handling, all study blood draws will be removed from the protocol except those that are for labs in order to determine if participant is healthy and can participate in the study (T0). If the participant attends the research study gynecological exam (which must be conducted in person and cannot be modified), this will be collected during the exam. If they instead provide their own gynecological records, the blood draw for labs will be performed by the coordinator at the participant's home or at the hospital.

Saliva samples. Saliva samples will now be collected for E2 and P4 assay. This will be collected by the participant in their home. All saliva sample materials will be given to participants with instructions during the first in-person contact during (T1) to be completed remotely. We have created collection documents and a log for participants to complete in. At visit T4, all tubes will be collected from the participant and taken back to the UNC Core laboratory for storage. Consent forms have been modified to reflect this change.

End of Study Feedback. We have expanded the information participants will be provided at the end of study participation. All participants who completed the study have the option to learn how their eating behaviors changed in response to the study medications. However, given the current pandemic we have expanded this to include a more comprehensive report vs overview as this detailed information could be immediately beneficial. This report will include how eating behaviors changed but now also include a discussion of (1) how this may translate to natural menstrual cycles (e.g., high

or low risk periods for symptoms); (2) strategies that can be used to manage symptoms; (3) triggers that may suggest a high risk period of the menstrual cycle is forthcoming (e.g., ovulation, mensuration); (4) additional resources and recommendations that may be useful based on the participants individual response. This will remain a permanent change to the study protocol. We have added additional text regarding this for interested participants on the study website and as part of the Qualtrics and phone/clinic screen.

COVID Risk. If a participant has direct or secondary contact with any suspected or confirmed cases of COVID-19 or experience any known symptoms of COVID-19, the study team will reschedule any scheduled in person study visits until the case is confirmed negative or until the subject has quarantined for at least 14 days from the first symptom.
